### Physician/Clinician Participants Inclusion Criteria

Participating sites must undergo a contracting procedure and agree to follow the study protocol as well as all terms of the study contract. Participating sites will be led by a physician / clinician (eg, nurse, nurse practitioner, physician assistant, etc.) who will serve as that site's PI/sub-PI. The participating PI/sub-PI must meet all the following inclusion criteria to participate in the study:

- Must be a healthcare provider with at least 60% of time spent in direct patient care
- Board-certified or eligible with a Specialty in Hematology or Hematology-Oncology (if hematologist-oncologist, at least 10% practice is dedicated to treatment of hemophilia)
- Currently manages at least 10 hemophilia A and/or B patients
- Must not be on the FDA debarment list

Protocol # B1821056  
Statistical Analysis Plan

Patient Participants Inclusion Criteria

Participants must meet all of the following inclusion criteria to be eligible for inclusion in the study:

- Willing and able to provide informed consent
- Diagnosed with hemophilia A or B
- Current disease severity is either moderately severe or severe with a clotting factor level of  $\leq 5\%$
- If suffering from hemophilia A, must be currently taking Xyntha (or another standard half-life treatment), Adynovate or Eloctate for at least six months.
  - If currently taking Adynovate or Eloctate, must have been switched from a standard half-life treatment and had been on that prior treatment for at least six months.
- If suffering from hemophilia B, must be currently taking BeneFIX or Alprolix for at least six months.
  - If currently taking Alprolix, must have switched from BeneFIX and had been on that prior treatment for at least six months.
- Infuse at least 3 times per month

In the event of a caregiver responding on behalf of the patient, the above inclusion criteria will be applied for the patient for whom the caregiver is responding.

Patient Participants Exclusion Criteria

Currently enrolled in a clinical trial and/or using investigational product for the treatment of his or her hemophilia

**2.3. Study Objectives**

The study's primary objective is to compare the dosing and resource utilization patterns of standard half-life treatments vs. extended half-life treatments for the management of hemophilia A and B

- Specifically, the dosing and resource utilization patterns of Xyntha (or other standard half-life treatments) vs. Adynovate or Eloctate (extended half-life) will be assessed for treatment of hemophilia A
- And similarly, the dosing and resource utilization patterns of BeneFIX (standard half-life) vs. Alprolix (extended half-life) will be assessed for treatment of hemophilia B

### **3. ANALYSIS SETS/ POPULATIONS**

#### **3.1. Full analysis set**

All physicians (N=30) and hemophilia A (N=150) and B (N=150) patients from the study will be available for analysis.

#### **3.2. Subgroups**

Subgroups will include the different treatment cohorts as defined above under “Treatment/cohort levels” and outlined again below.

- Patients on Xyntha (or other standard half-life treatments) vs. Adynovate or Eloctate (extended half-life treatments) for treatment of hemophilia A
- Patients on BeneFIX (standard half-life treatment) vs. Alprolix (extended half-life treatment) for treatment of hemophilia B

### **4. ENDPOINTS AND COVARIATES**

#### **4.1. Efficacy/ Effectiveness Endpoint(s)**

##### Physician Participants:

##### *Physician/Practice Characteristics*

- Primary medical specialty
- Board certification
- Percentage of time spent in direct patient care
- Percentage of their practice dedicated to the treatment of hemophilia
- Number of moderate to severe hemophilia A and B patients currently managed
- Number of hemophilia A and B patients currently participating in clinical trials
- Insurance plans accepted

##### *Patient Treatment Pattern (from patient chart)*

- Current and previous hemophilia treatment
- Reasons for discontinuation
- Duration of treatment used
- Whether prescription was prophylaxis or on-demand
- Number of infusions per month prescribed

Protocol # B1821056  
Statistical Analysis Plan

- Frequency of doctor visits for management of hemophilia

*Patient Demographics (from patient chart)*

- Age
- Sex
- Race
- Weight
- Height
- Health insurance type

*Patient Clinical Profile (from patient chart)*

- Age of diagnosis
- Primary symptoms
- Disease severity
- Joint health score
- Comorbidities

Patient Participants (self-reported or caregiver reported):

*Patient Demographics*

- Sex
- Age
- Race/ethnicity
- Marital status
- Household income
- Education\*
- Employment status\*
- Health insurance type

Protocol # B1821056  
Statistical Analysis Plan

- Healthcare insurer
- Pharmacy insurer

\*In the case of caregivers responding, caregiver's education and employment will also be collected.

*Patient Clinical Profile*

- Disease severity
- Clotting factor level

*Patient Treatment*

- When are infusions done
- Number of infusions in a typical month
- Previous and current hemophilia treatments
- Duration of previous and current hemophilia treatments used
- Recent factor use behavior
- Whether participated in clinical trials within the past 12 months

*Physician Patient Relationship*

- Patient's relationship with his/her physician in regards treatment decisions for hemophilia rated as either paternalistic, informative, interpretive, or deliberate depending upon which relationship description the patient selects.

*Validated Scales for Health-Related Quality of Life*

*Global health-related quality of life scales*

36 Item Short Form Health Survey (SF-36; adult): The SF-36v2 is a multipurpose, generic health status instrument comprised of 36 questions. These items map onto eight health domains: physical functioning, physical role limitations, bodily pain, general health, vitality, social functioning, emotional role limitations, and mental health. In addition to these eight health domains, there are two component summary scores: the physical component summary (PCS) and the mental component summary (MCS).

10 Item Short Health Survey (SF-10; caregiver reported for child): A-parent completed survey that contains 10 questions adapted from the Child Health Questionnaire (CHQ). The SF-10 assesses a wide range of domains and is scored to produce a physical and psychosocial health summary score. This survey is intended for children aged 5 through 18.

Protocol # B1821056  
Statistical Analysis Plan

*Hemophilia-specific health-related quality of life scales*

Hemophilia-Specific Quality of Life Index for Adults (HAEM-A-QOL; adult): quality of life measure for adults, that examines 10 domains (46 items) and validated in English. Domains include physical, emotional, social, functional, mental, and treatment-related.

Hemophilia-Specific Quality of Life Index (HAEMO-QOL; caregiver reported for child): Quality of life measure for children. This is the parent-reported short version that has a 16-item and a 35-item index for children age 4-7 and 8-17 respectively.

**Health Insurance Claims Data Submitted by Patients**

- Total services and healthcare costs (healthcare visits, factor)
- Hemophilia-specific services and costs (healthcare visits, factor)

An allocation algorithm for determining how cost groupings will be defined will be developed with discussion with Pfizer.

**4.2. Safety Endpoints**

This study does not aim to collect data on clinical endpoints on individual patients. However, safety information may be identified during the course of data collection. Any safety information for an individual patient that is volunteered by a study participant (eg, health care professional, lay person) during the course of this research will be reported as described in the study protocol.

**4.3. Other endpoints**

None.

**5. HANDLING OF MISSING VALUES**

Complete data from the physician CRF and patient questionnaire are available for all items except those allowing, eg, a “don’t know” response. In such cases, if those variables are included as covariates in multivariable models or as outcome measures in bivariate analysis, missing values will be included as a separate, defined category. If those variables are analysed as outcomes, respondents with missing data will be excluded from analysis (and the subsample for analysis will be reported).

**6. STATISTICAL METHODOLOGY AND STATISTICAL ANALYSES**

**6.1. Statistical methods**

**6.1.1. *Descriptive Analyses***

Descriptive statistics (means and standard deviations for continuous variables and frequencies and percentages for categorical variables) will be reported for all study measures on the total sample and subgroups. This analysis of the distributions will be a part of testing of model assumptions and will help inform the appropriate modeling techniques.

### ***6.1.2. Bivariate Analyses***

Bivariate (BV) comparisons and descriptives can help provide initial insight into the dosing, health-related quality of life, resource utilization, and cost patterns associated with different hemophilia treatments (standard half-life vs. extended half-life). Bivariate comparisons, using chi-square tests or one-way ANOVA for categorical and continuous variables, respectively, will be conducted for each hemophilia subgroup (A and B).

The BV results will be used to feed into a more robust multivariable (MV) analysis to create a model to estimate health-related quality of life, resource utilization and costs, while controlling for covariates, associated with different hemophilia treatments.

### ***6.1.3. Multivariable Analyses***

#### Generalized Linear Models

The type of GLM will be chosen on the basis of the distributions of the outcome variables of interest. For example, GLMs specifying a normal distribution and identity function will be used with mostly normally distributed variables (such as is typically the case with SF-36v2 HRQoL measures), whereas GLMs specifying a negative binomial distribution and log-link function will be used with highly positively skewed variables (such as is typically the case with healthcare resource utilization measures). Model fits will be examined to aid with model selection. For example, Poisson models may be attempted first, with highly skewed outcomes, but negative binomial models will also be tested to see if fits improve substantially when including the estimated relationship between mean and variance. Corrections to the standard errors will be implemented automatically to compensate for model underdispersion. In the case of normal distributions, GLMs are recommended, as they are more robust than ordinary least squares (OLS) models to minor deviations from normality.

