**Table 1. Study Sample**

	Sample Size	
	Xyntha	Eloctate or Adynovate
Hem A Patients / Caregivers of Hem A Patients	75	75
Total Hem A	150	
	Alprolix	BeneFIX
Hem B Patients / Caregivers of Hem B Patients	75	75
Total Hem B	150	
TOTAL	300	

This study will compare Xyntha vs. Eloctate /Adynovate among hemophilia A patients and Alprolix vs. BeneFIX among hemophilia B patients. For a mean difference comparing two independent means with the anticipated sample sizes (75 vs. 75; 150 total) with  $\alpha=0.05$ , two-sided, 80% power, the expected minimal detectable effect (MDE) would be Cohen's  $d=0.46$ . This study with the anticipated sample size is powered to detect at least a moderate effect size.

The inclusion and exclusion criteria for physicians and patients are specified below.

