### 6.2.3. Multivariable Analyses

For hemophilia A and hemophilia B cohorts separately, multivariable regression models will be conducted with treatment group (standard half-life vs. extended half-life) as the predictor of each outcome (ie, number of infusions, health-related quality of life, healthcare resource utilization, total healthcare costs, total Rx costs, hemophilia healthcare costs, hemophilia Rx costs) adjusting for the demographic and health history variables that have been identified as relevant covariates in bivariate analyses.

Generalized linear models will be used specifying the appropriate distribution (ie, negative binomial for skewed variables such as healthcare resource use and cost variables; identity link function for normally distributed variables such as health-related quality life). A regression summary results table with adjusted means, 95% CIs, standard errors, and p-values will be produced ([Table 8](#)).

**Table 8. Example regression summary table. Outcomes among hemophilia A patients by standard half-life vs. extended half-life treatment (adjusted for covariates). Note: a similar table would be created for hemophilia B patients.**

Outcome	Standard Half-Life				Extended Half-Life				p-value
	Mean	SE	Lower 95% CI	Upper 95% CI	Mean	SE	Lower 95% CI	Upper 95% CI	
Number of infusions per month									
SF-36 MCS/ SF-10 psychosocial									
SF-36 PCS / SF-10 physical									
HEAM-A-QOL / HAEMO-QOL									
Total Healthcare visits									
Total Healthcare costs									
Total Rx costs									
Hemophilia healthcare visits									
Hemophilia healthcare costs									
Hemophilia Rx costs									

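### The GLM section names a standard-error correction for underdispersion only and credits normal GLMs with robustness they lack; sandwich standard errors would close the narrow gaps that the negative binomial plan leaves

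*SAP*

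**What the plan says.** The Generalized Linear Models text is the same in SAP 6.1.3 and Protocol 8.7. It makes four statements that bear on standard errors.

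- For skewed outcomes: "GLMs specifying a negative binomial distribution and log-link function will be used with highly positively skewed variables".
- Poisson may be tried first, in which case "negative binomial models will also be tested to see if fits improve substantially when including the estimated relationship between mean and variance". No criterion for a substantial improvement is given.
- Immediately afterwards: "Corrections to the standard errors will be implemented automatically to compensate for model underdispersion". No method is named.
- For normal outcomes: "GLMs are recommended, as they are more robust than ordinary least squares (OLS) models to minor deviations from normality".

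SAP 6.2.3 then assigns models to outcomes: "negative binomial for skewed variables such as healthcare resource use and cost variables" and "identity link function for normally distributed variables such as health-related quality life". The number of infusions is listed there as an outcome and heads Table 8, but no distribution is assigned to it by name. Neither document mentions sandwich standard errors, Pearson scaling for overdispersion, or an unequal-variance analysis.

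**The concern.** The correction sentence follows directly on a discussion of skewed counts. The usual failure there is variance above the mean, which makes Poisson standard errors too small. A correction for underdispersion acts only when variance is below the mean and does nothing in the other case. A programmer who follows the text literally would therefore add no protection where it is most often needed.

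The robustness sentence has a different fault. It gives the quality-of-life models a safeguard that the method cannot supply, so a reader may think that departures from the model have been dealt with.

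At stake are the p-values and confidence intervals of Table 8. Its outcomes include infusions, visits and costs, which carry the primary objective on dosing and resource use.

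**Working it through.** **Inputs from the documents.** 75 v 75 in each hemophilia type, two-sided alpha 0.05, 80% power, detectable effect d = 0.46 (SAP 2.2).

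**Assumed, because the documents give no value.** Variance/mean 1.25 to 3; count means 4 and 10; AIC rules for the switch from Poisson; lognormal costs with log-SD 1; SD ratios 2 and 3; unequal group sizes. The simulations have no covariates and no true treatment effect.

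**1. The plan's own figure.** (1.960 + 0.842) × √(2/75) = 0.457; the noncentral t gives 0.460. The stated 0.46 reproduces, and nothing below changes it.

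**2. Normal GLM against OLS.** Both were fitted to the same skewed data (n = 150, treatment plus one covariate). The largest difference was 0 in the coefficients and 0 in the standard errors (treatment SE 1.1538 in both). Software that uses the maximum-likelihood scale would give slightly smaller errors, by √(147/150) = 0.990, which is not added robustness.

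**3. What an underdispersion correction does.** The standard error is multiplied by √φ when φ < 1: 0.71 at φ = 0.5 and 0.50 at φ = 0.25. When φ > 1 nothing changes.

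**4. Poisson first, then negative binomial if fit improves enough.** Null simulations at 75 v 75 with 2,000 to 4,000 replicates; Monte Carlo error is about √(0.05 × 0.95/2,000) = 0.5 points or less.

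| Variance/mean | Switch if AIC gain > 10: negative binomial chosen | Type I error | Switch if AIC is lower: type I error |
|---|---|---|---|
| 1.25 | 6 to 8% | 7.3 to 8.7% | 5.6 to 6.8% |
| 1.5 | 53 to 55% | 7.1 to 7.6% | 4.7 to 5.8% |
| 2 to 3 | 99 to 100% | 4.8 to 6.1% | 4.7 to 6.1% |

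The ranges cover both means and repeated runs. In round terms, the error at ratios 1.25 to 1.5 is 7.5 to 8.5% under the strict rule and 5.5 to 6% under the lenient one. Sandwich errors gave 4.5 to 6.2% throughout.

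**5. Negative binomial on continuous costs.** With a large mean, the negative binomial behaves like a gamma model with shape k. For lognormal data with log-SD 1, the fitted k solves ln k − ψ(k) = 1²/2 (ψ is the digamma function), so k = 1.138. The model-based squared coefficient of variation is 1/k = 0.879. The true value is e − 1 = 1.718. The standard error is therefore √(0.879/1.718) = 0.715 of the correct size, and the large-sample type I error is 2 × (1 − Φ(1.96 × 0.715)) = 16%. Simulation at 75 v 75 gave about 13%, against 5.5% with sandwich errors; a repeat of 4,000 replicates gave 15% and 6.5%.

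**6. Unequal variance in a normal model** (20,000 replicates).

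| Group sizes | SDs | Equal-variance errors | Unequal-variance errors |
|---|---|---|---|
| 75:75 | 1, 2 | 5.0% | 5.0% |
| 75:75 | 1, 3 | 5.0% | 5.0% |
| 100:50 | 1, 2 | 11.5% | 5.5% |
| 60:30 | 1, 2 | 11.3% | 5.5% |
| 50:100 | 1, 2 | 1.4% | 4.7% |

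**The case against.** The strongest objection is that the plan already models overdispersion. Negative binomial regression is named for skewed variables in 6.1.3 and assigned to resource use and costs in 6.2.3, and the comparison with Poisson is itself a check for overdispersion. This stands. A reader might infer from the correction sentence that overdispersed outcomes are left unprotected; the documents do not support that. On simulated negative binomial counts with dispersion 2 to 11, the planned model held type I error at 5.5 to 6.1%.

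A reader might also compute the error of an unscaled Poisson model, 2 × (1 − Φ(1.96/√φ)), which is 11%, 17% and 26% at φ = 1.5, 2 and 3. Those figures describe an analysis with no negative binomial comparison, which the plan does not propose, so they are not the expected harm.

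Nor would the correction shrink standard errors under overdispersion: it is inactive there. It could even be deliberate. Eligibility requires at least three infusions a month, so infusion counts could vary less than Poisson. At φ = 0.5 an unscaled Poisson test has a type I error of only 0.6%, and a correction would be right. Equally, the word may be a slip for its opposite. The text does not settle which, and it is the same in both documents.

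The excess in step 4 depends on how a substantial improvement is read. Under a lower-AIC rule it nearly disappears, so a stated rule would also deal with most of that part. It would not help with costs, where the question is whether the negative binomial variance form fits at all.

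For quality of life, the documents' claim concerns non-normality rather than unequal variance, and Protocol 8.2 plans monitoring to keep the cohorts equal. No inflation appears at 75:75.

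**Conclusion.** The point holds in a limited form. Two sentences in both documents need correction: the dispersion correction names one direction only and no method, and the GLM-over-OLS claim is false. Neither changes an estimate.

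The exposure that remains, in order of size under the stated assumptions:

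- **Costs.** About 13% type I error against 5.5% with sandwich errors, if costs are roughly lognormal with log-SD 1. The documents say nothing about the cost distribution.
- **Mildly overdispersed counts.** About 7.5 to 8.5% at variance/mean 1.25 to 1.5 if the switch needs an AIC gain above 10, about 5.5 to 6% under a lower-AIC rule, and about 5% at ratios of 2 or more.
- **Quality of life.** Nothing at 75:75. Inflation to about 11% needs roughly 2:1 group sizes with twice the SD in the smaller group. Cohort targets are approximate, and SAP section 5 excludes respondents with missing outcomes, so imbalance is possible but not shown. The SAP's warning about low sample size concerns claims data, not these scales.

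**What to change.** In SAP 6.1.3 and Protocol 8.7, replace the correction sentence with: *All GLMs will use sandwich (robust) standard errors, valid under over- or underdispersion.* Add that the normal models will use the HC3 form. Delete the claim that GLMs are more robust than OLS.

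This keeps the planned models and the 0.46 detectable effect. It covers dispersion in either direction, so the meaning of the present word no longer matters, and the validity of the standard errors depends much less on whether Poisson or negative binomial is chosen. A numerical rule for that choice would still be useful, but it does not replace the robust errors.

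The cost is two sentences and a software option. Intervals will be somewhat wider where data are overdispersed, and sandwich errors are slightly imprecise in small samples, which matters if few patients supply claims. The change leaves the unadjusted one-way ANOVAs in SAP 6.1.2 as they are.

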## **6.2. Statistical Analyses**

### ***6.2.1. Descriptive Analyses***

Descriptive analyses will serve to characterize the physician sample and the hemophilia A and B sample. Specifically:

- Physician characteristics (eg, medical specialty, percentage of time in patient care) will be examined with means and standard deviations for continuous variables and frequencies and percentages for categorical variables
- Patient characteristics (eg, age, sex, income) will be examined with means and standard deviations for continuous variables and frequencies and percentages for categorical variables

### ***6.2.2. Bivariate Analyses***

Differences among hemophilia patients on standard half-life vs. extended half-life treatments (hemophilia A: Xyntha vs. Adynovate or Eloctate; hemophilia B: Benefix vs. Alprolix) will be made with respect to demographics variables to assess for potential covariates to include

Protocol # B1821056  
 Statistical Analysis Plan

in subsequent modeling (*Table 2*). Chi-square tests and one-way ANOVAs will be used for categorical and continuous outcomes, respectively. Additionally, differences among treatment groups will also be made with respect to hemophilia specific characteristics (eg, disease severity, symptoms), attitudes towards infusions and physician relationship and outcomes (eg, number of infusions, health-related quality of life, healthcare resource utilization, total healthcare costs, total Rx costs, hemophilia healthcare costs, hemophilia Rx costs) to assess unadjusted differences using one-way ANOVAs (*Table 3-Table 7*).

These analyses will be conducted separately for hemophilia A and hemophilia B patients.

Note that healthcare costs and Rx costs will be obtained from claims data and may be limited by sample size as not every patient may be willing to provide that data. If sample sizes are very low, bivariate and multivariable comparisons may not be conducted; descriptive statistics will be provided instead.

**Table 2. Example bivariate Table: Patient demographics among hemophilia A patients by standard half-life vs. extended half-life treatment. Note: a similar table would be created for hemophilia B patients.**

	Treatment Group							
	Standard Half-Life		Extended Half-Life		Total			
	% / Mean	N/ SD	% / Mean	N/ SD	% / Mean	N/ SD		
Age								
Gender	Male							
	Female							
Marital Status	Married/partnered							
	Single/divorced/widowed							
	Declined to answer							
Race/Ethnicity	Non-Hispanic White							
	Non-Hispanic Black							
	Hispanic							
	Other ethnicity							
Education	4 years							
	Less than 4 years							
Household income	<25K							
	\$25K to <50K							
	\$50K to <75K							
	\$75K or more							
	Declined to answer							
Employment Status	Employed							
	Not Employed							

Protocol # B1821056  
 Statistical Analysis Plan

**Table 2. Example bivariate Table: Patient demographics among hemophilia A patients by standard half-life vs. extended half-life treatment. Note: a similar table would be created for hemophilia B patients.**

		Treatment Group							
		Standard Half-Life		Extended Half-Life		Total			
		% / Mean	N/ SD	% / Mean	N/ SD	% / Mean	N/ SD		
	Student								
Geographic Region	South								
	Northeast								
	Midwest								
	West								
Insurance	Coverage through employer								
	Coverage through spouse's/partner's employer								
	Coverage through parent's or legal guardian's employer								
	Individual/Family Plan- State Health Exchange								
	Individual/Family Plan- Self-purchased								
	Medicaid (MediCal for California)								
	Medicare								
	Veterans Administration (VA)/CHAMPUS								
	TRICARE								
	Not sure								
Healthcare insurer	Aetna								
	Anthem (Blue Cross and Blue Shield, Empire Blue Cross, Amerigroup, UniCare, CareMore, Wellpoint)								
	Centene								
	Cigna								
	Health Net								
	Human								
	Kaiser Permanente								
	Magellan Health								

Protocol # B1821056  
 Statistical Analysis Plan

**Table 2. Example bivariate Table: Patient demographics among hemophilia A patients by standard half-life vs. extended half-life treatment. Note: a similar table would be created for hemophilia B patients.**

	Treatment Group							
	Standard Half-Life		Extended Half-Life		Total			
	% / Mean	N/ SD	% / Mean	N/ SD	% / Mean	N/ SD		
Molina Healthcare								
UnitedHealth Group								
WellCare Health Plans								
Other, specify								
Different insurer covering prescription or pharmacy benefits?	Yes, different insurer for prescriptions							
	No, same insurer as medical							
	Don't know							
On patient assistance program for hemophilia medication?	Yes							
	No							
	Don't know							

**Table 3. Example bivariate table: Patient health characteristics, disease characteristics, and treatment history among hemophilia A patients by standard half-life vs. extended half-life treatment (from patient chart). Note: a similar table would be created for hemophilia B patients.**

	Treatment Group							
	Standard Half-Life		Extended Half-Life		Total			
	% / Mean	N/ SD	% / Mean	N/ SD	% / Mean	N/ SD		
BMI category	BMI: underweight							
	BMI: normal weight							
	BMI: overweight							
	BMI: obese							
	Declined to answer							
When diagnosed with hemophilia	Infancy 0-12 months							
	Toddler 1-3 years							
	Preschool 3-5 years							

Protocol # B1821056  
 Statistical Analysis Plan

**Table 3. Example bivariate table: Patient health characteristics, disease characteristics, and treatment history among hemophilia A patients by standard half-life vs. extended half-life treatment (from patient chart). Note: a similar table would be created for hemophilia B patients.**

	Treatment Group							
	Standard Half-Life		Extended Half-Life		Total			
	% / Mean	N/ SD	% / Mean	N/ SD	% / Mean	N/ SD		
Grade school 5-12 years Teen 12-18 years Young adult 18-21 years <21 years Don't know								
Comorbidities	Joint disease High blood pressure High cholesterol Heart disease Diabetes HIV Hepatitis Other (specify) None of above							
Currently taking medication for joint disease?	Yes No							
Current disease severity	Moderate hemophilia (1-5% factor level) Severe hemophilia (Less than 1% factor level)							
Current primary symptoms	Excessive bleeding after cuts, injuries, or medical procedures Unexplained nosebleeds Excessive bruising Joint pain, swelling, or tightness Blood in stool or urine Other None of the above							
Current joint	Score							

Protocol # B1821056  
 Statistical Analysis Plan

**Table 3. Example bivariate table: Patient health characteristics, disease characteristics, and treatment history among hemophilia A patients by standard half-life vs. extended half-life treatment (from patient chart). Note: a similar table would be created for hemophilia B patients.**

		Treatment Group							
		Standard Half-Life		Extended Half-Life		Total			
		% / Mean	N/ SD	% / Mean	N/ SD	% / Mean	N/ SD		
health score	Don't know								
Joint health score system	Hemophilia Joint Health Score (HJHS)  World Federation of Hemophilia (WFH) score  Other joint scoring system (specify)								
Current factor	Advate  Adynovate  Afstyla  Eloctate  Helixate FS  Hemofil M  Kogenate FS  Kovaltry  Monoclate-P  Novoeight  Nuwiq  Recombinate  Xyntha solofuse  Other, specify								
How factor prescribed	Prophylactically  On-demand  Both prophylactically and on-demand								
Duration of current factor prescribed									
Number of infusions per month									
Prior treatment	Advate  Adynovate  Afstyla  Eloctate  Helixate FS  Hemofil M								

Protocol # B1821056  
 Statistical Analysis Plan

**Table 3. Example bivariate table: Patient health characteristics, disease characteristics, and treatment history among hemophilia A patients by standard half-life vs. extended half-life treatment (from patient chart). Note: a similar table would be created for hemophilia B patients.**

	Treatment Group						p-value	
	Standard Half-Life		Extended Half-Life		Total			
	% / Mean	N/ SD	% / Mean	N/ SD	% / Mean	N/ SD		
Kogenate FS								
Kovaltry								
Monoclate-P								
Novoeight								
Nuwiq								
Recombinate								
Other, specify								
Was not taking another treatment previously								
Duration of former factor prescribed								
Reasons for discontinuation	Cost/insurance coverage issues							
	[IF PATIENT IS UNDER 18] Patient developed inhibitors to treatment							
	Doctor recommendation							
	Patient preferred a different infusion frequency							
	Other							
	Don't know							
Frequency of visits (non-infusion)	Several times a month							
	Once a month							
	Every three months							
	Every six months							
	Once a year							
	Less than once a year							

Protocol # B1821056  
 Statistical Analysis Plan

**Table 4. Example bivariate table. Patient health characteristics, disease characteristics, and treatment history among hemophilia A patients by standard half-life vs. extended half-life treatment (patient-reported). Note: a similar table would be created for hemophilia B patients.**

		Treatment Group							
		Standard Half-Life		Extended Half-Life		Total			
		% / Mean	N/ SD	% / Mean	N/ SD	% / Mean	N/ SD		
Severity	Mild hemophilia Moderate hemophilia Moderately severe hemophilia Severe hemophilia								
Clotting factor level	6% to 40% 1% to 5% Less than 1%								
Current treatment	Advate Adynovate Afstyla Eloctate Helixate FS Hemofil M Kogenate FS Kovaltry Monoclate-P Novoeight Nuwiq Recombinate Xyntha solofuse Other, specify								
Duration of current factor prescribed									
When infuse	On regular basis to prevent bleeding episodes Whenever or as needed when there is a bleeding episode Both, on a regular basis to prevent bleeding episodes as well as whenever as needed when there is a bleeding episode								
Prior treatment	Advate Adynovate								

Protocol # B1821056  
 Statistical Analysis Plan

**Table 4. Example bivariate table. Patient health characteristics, disease characteristics, and treatment history among hemophilia A patients by standard half-life vs. extended half-life treatment (patient-reported). Note: a similar table would be created for hemophilia B patients.**

	Treatment Group							
	Standard Half-Life		Extended Half-Life		Total			
	% / Mean	N/ SD	% / Mean	N/ SD	% / Mean	N/ SD		
Afstyla								
Eloctate								
Helixate FS								
Hemofil M								
Kogenate FS								
Kovaltry								
Monoclate-P								
Novocight								
Nuwiq								
Recombinate								
Other, specify								
Was not taking another treatment previously								
Duration of former factor prescribed								
Clinical trials for receiving treatment	Yes							
	No							

**Table 5. Example bivariate table. Health-related quality of life among hemophilia A patients by standard half-life vs. extended half-life treatment (patient-reported). Note: a similar table would be created for hemophilia B patients.**

	Treatment Group							
	Standard Half-Life		Extended Half-Life		Total			
	Mean	SD	Mean	SD	Mean	SD		
for adults								
SF-36 Physical Component Summary Score								
SF-36 Mental Component Summary Score								
HAEM-A-QOL)								
caregiver reported for child								
SF-10 Physical summary score								
SF-10 Psychosocial health summary score								
HAEMO-QOL								

Protocol # B1821056  
 Statistical Analysis Plan

**Table 6. Example bivariate table. Patients' attitudes on factor use and physician relationship among hemophilia A patients by standard half-life vs. extended half-life treatment. Note: a similar table would be created for hemophilia B patients.**

		Treatment Group						p-value	
		Standard Half-Life		Extended Half-Life		Total			
		%	N	%	N	%	N		
Frequency of extra infusion used	Never								
	2 times								
	3 times								
	4 times or more								
Reasons for using extra infusion	Bleeding episode								
	Wanted additional protection before sport/activity								
	Felt pain (thought it was bleed)								
	Wanted extra protection for no specific reason								
Frequency of dose higher than prescribed	Never								
	1-2 times								
	3-4 times								
	5-6 times								
	7 or more times								
Reasons for higher dosing	Wanted additional protection before sport/activity								
	Felt pain (thought it was bleed)								
	Wanted extra protection for no specific reason								
Physician relationship	The physician is the professional; 'I' / 'we' follow his/her recommendations. 'I' / 'We' see the physician as the expert who knows what's best for 'me' / 'my child'. The physician makes the final decision.								

Protocol # B1821056  
Statistical Analysis Plan

The physician informs 'me' / 'me and my child' of the different treatment plans available to 'me' / 'my child' and lets 'me' / 'us' select the final treatment. The physician provides technical expertise but 'I' / 'we' make the final decision on treatment.							
The physician works with 'me' / 'me and my child' to understand 'my' / 'our' values and what 'I' / 'we' want out of the treatment and then discusses the different treatment options available to 'me' / 'us' based on 'my' / 'our' needs before we make the joint decision for 'me' / 'my child'. 'I' / 'We' see the physician as a counselor.							
The physician works with 'me' / 'us' to understand 'my' / 'our' values and what 'I' / 'we' want out of the treatment, and goes over all 'my' / 'our' treatment options and his/her recommendations so that 'I' / 'we' can make the best possible decision. 'I' / 'We' see the physician as a teacher or friend.							

**Table 7. Example bivariate table. Healthcare resource use and associated costs among hemophilia A patients by standard half-life vs. extended half-life treatment (insurance-claims). Note: a similar table would be created for hemophilia B patients.**

	Treatment Group						p-value	
	Standard Half-Life		Extended Half-Life		Total			
	Mean	SD	Mean	SD	Mean	SD		
Total number of healthcare visits								
Total number of healthcare costs								
Total Rx costs								
Total number of Hemophilia-specific visits								
Total number of Hemophilia-specific costs								
Total Hemophilia Rx costs								

